variably according to the patient's IMDC (International mRCC Database Consortium) risk score. IMDC represents a large collection of real-world data (RWD) on patients with advanced kidney cancer treated with targeted therapies [7,8]. IMDC combinations available for favourable risk patients include pembrolizumab + axitinib, nivolumab + cabozantinib and pembrolizumab + lenvatinib; for intermediate or poor risk patients the combination of ipilimumab and nivolumab is recommended in addition to the aforementioned three combinations. None of the recommended first-line treatment options have been compared head-to-head but all of the pivotal clinical studies have sunitinib monotherapy as a control, a former standard-of-care (SoC). The current second and later line treatment recommendations include VEGFR-TKI monotherapies, such as pazopanib and sunitinib, but will likely be reshaped in the coming years as clinical evidence on the optimal treatment sequence is accumulated.

The prognostic model constructed by the IMDC has been used to stratify patients in contemporary clinical trials and to provide risk-directed treatment selection in everyday clinical practice. The IMDC prognostic model contains six independent predictors of poor survival, which are: Karnofsky performance status of less than 80%, less than 1 year from diagnosis to treatment, anaemia (haemoglobin concentration <lower limit of normal), hypercalcaemia (corrected calcium concentration >upper limit of normal), neutrophilia (neutrophil count >upper limit of normal), and thrombocytosis (platelet count >upper limit of normal). An IMDC risk score is determined for a patient according to the number of poor prognostic factors the patient has; favourable risk patients have 0 factors; intermediate risk patients have one or two factors; and poor risk patients have three or more factors.

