- Treatment initiation for mRCC (sunitinib, pazopanib, cabozantinib, ipilimumab, nivolumab)

When analyzing the treatment outcomes, index is defined as the date of the treatment initiation.

End of follow-up (whichever of the following occurs first):

- Death
- Moving outside of HDSF
 - Approximated using data of healthcare contacts; no contacts to specialty care of HDSF within 2 years (patient censored at the last recorded visit)
- End of study (31.12.2021)

Length of follow-up (in years): ('end of follow-up' – 'index' + 1)/365.25

Definitions for characteristics cohort

Index:

- For mRCC patients, same as for the mRCC cohort (i.e. approximated metastasis date)
- For RCC patients, the date of the first record of RCC diagnosis (ICD-10: C64)

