7.2.3. Patient stratification

Analyses will be stratified by:

- IMDC risk category (defined at the initiation of the first treatment for the metastatic RCC; see Table 1 and listing below for definitions)
 - Applied to all primary and secondary objectives
- Treatment line
 - Applied to primary objective 2 and 3

IMDC risk factors (each criterion accounts for +1 for the risk score):

1. Less than a year from time of initial RCC diagnosis to initiation of treatment for the metastatic RCC

2. Performance status* <80% (Karnofsky)
3. Hemoglobin* below normal (women < 117 g/l; men < 134 g/l)
4. Serum calcium* above normal (> 2.51 mmol/l)
5. Neutrophiles* above normal (> 6.3 x 10⁹/l)
6. Thrombocytes* above normal (> 350 x 10⁹/l)

** for performance status and laboratory values data of ± 3 months around the treatment initiation will be utilized due to possibly sparse data. If multiple records are available, the record closest to the treatment initiation will be utilized.*

Table 1. IMDC risk scores and categories based on two different approaches depending on the data coverage

	IMDC risk category	Total score of IMDC risk factors	Explanations/missing values
Option 1*	Favorable risk	0	no missing values allowed
	Intermediate risk	1-2	1) total score = 1; max 1 risk factor allowed to have missing value 2) total score = 2; no missing values allowed
	Poor risk	3 or more	max 3 risk factors allowed to have missing values
	Unknown risk**	-	when none of the above risk categories can be assigned
Option 2*	Appear favorable	0	all non-missing values for the risk factors indicate favorable risk max 3 risk factors allowed to have missing values
	At least intermediate	≥1	at least one risk factor criterion is met max 3 risk factors allowed to have missing values
	Poor	≥3	at least three risk factor criteria is met max 3 risk factors allowed to have missing values
	Unknown**	-	when none of the above risk categories can be assigned, i.e. more than 3 risk factors have missing value

** If small number of missing values is observed, the option 1 will be selected. If large number of missing values is observed and thus majority of patients were to belong to the “unknown” group of the option 1, the option 2 will be selected. The selection will be done after the data release and monitoring of data coverage.*

*** Patients with unknown risk category, will be analysed as own patient group.*

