7.7. Data analysis

Data will be analyzed using primarily descriptive measures, which include mean/median values for continuous variables and proportions for categorical variables. Costs will be estimated using data of visits, hospitalizations, procedures, etc. and utilizing publicly available price listings. For treatment outcomes, Kaplan-Meier estimates and/or corresponding time to event competing risk models will be utilized.

All analyses will be reported for the whole advanced/metastatic RCC patient population and stratified by the IMDC risk score. Additionally, treatment patterns and treatment outcomes will be reported by treatment lines.

Analyses are based on structured data, with the exception for potential text-mining of IMDC risk score or its components.

Due to the retrospective nature of the study, missing and/or incomplete data is expected in some of the medical records. Patients' records will not be excluded because of missing values, and missing data will not be imputed, i.e. the data will be analyzed as they are recorded in the electronic medical records. The proportion of missing values per variable will be reported.

Analyses will be performed using R, a language and environment for statistical computing, in Rstudio-server environment.

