7.7.4. Morbidity

Secondary objective 1:

Morbidity will be assessed using data of co-diagnoses, procedures, and medications before and after diagnosis of advanced/metastatic RCC using all available data (ICD-10, procedure codes, and ATC-codes) in baseline and during the follow-up, respectively. The number (N) and proportion (%) of patients with each morbidity will be reported.

The list of morbidities of interest are:

- co-diagnoses using ICD-10 codes
 - especially interest of infections (ICD-10: A00*-B99*) and hypertension (ICD-10: I10)
- procedures related to kidneys
 - all KA* (kidneys and pelvis of kidneys) and KA_* (diagnostic radiology of kidney and pelvis of kidneys) procedures codes
- use of antibiotics (ATC-code: J01*, J02* and J04*) and antihypertensive medication (ATC-code: C02*)

If data coverage seems low, use of antibiotics and antihypertensives can be used as a proxy for infections and hypertension, respectively, along with the diagnosis (ICD-10) data.

Therefore, diagnoses and medications will be analyzed as a combination instead of separately.

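### Post-index morbidity is reported only as N (%) over unequal follow-up, so the contrast between IMDC strata is distorted by survival time

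*Combined protocol and SAP*

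**What the plan says.** Section 7.7.4 assesses co-diagnoses, procedures and medications before and after the mRCC diagnosis, "using all available data (ICD-10, procedure codes, and ATC-codes) in baseline and during the follow-up, respectively". The only summary it names is this: "The number (N) and proportion (%) of patients with each morbidity will be reported".

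Section 7.2 defines the observation time: "End of follow-up (whichever of the following occurs first" of death, moving away (approximated by two years without specialty-care contact) and 31.12.2021. Metastatic disease may be identified at any time from 1.1.2010 to 31.12.2021 (7.2.1), so follow-up can run from near zero to about 12 years.

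On strata, section 7.2.3 says of the IMDC category: "Applied to all primary and secondary objectives". Section 7.7 repeats it: "All analyses will be reported for the whole advanced/metastatic RCC patient population and stratified by the IMDC risk score". Section 5 describes what the category measures: "The IMDC prognostic model contains six independent predictors of poor survival".

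Methods that handle unequal follow-up are given to other objectives. Section 7.7 says: "For treatment outcomes, Kaplan-Meier estimates and/or corresponding time to event competing risk models will be utilized". Section 7.7.5 gives resource use patient-year scaling, year-by-year costs over the first five years, and bootstrap confidence intervals. The limitations in 7.9 do not mention unequal follow-up.

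**The concern.** The chance that a patient has at least one recorded infection or antibiotic course rises with time under observation. IMDC strata are expected to differ in survival, hence in observation time. Side-by-side percentages by stratum would then differ even if morbidity occurred at the same rate in each. A real excess in poor-risk patients could look absent, or look like a deficit.

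At stake is the descriptive reading of secondary objective 1 by risk category. No between-stratum test is specified for morbidity, so no error rate is affected.

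**Working it through.** **The plan's own figure.** The only size given is the mRCC cohort (7.5): 1,100 × 0.20 = 220 and 1,100 × 0.50 = 550. Both reproduce. Secondary objective 1 uses only the treated subset. The plan states no survival or morbidity rate.

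**Assumed inputs (none from the documents).** Constant first-event rate r = 0.3 per patient-year in every stratum; exponential survival with median m years; medians for poor/intermediate/favourable of 8/20/40 months, or closer together at 12/20/30 months. Censoring is taken as uniform over 0–12 years, to mirror entry over 2010–2021 with a fixed end.

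**Formulas.** Let λ = ln 2 / m and a = r + λ.
- Proportion ever recorded: (r/a) × [1 − (1 − e^(−12a))/(12a)]
- 12-month cumulative incidence with death competing: (r/a) × (1 − e^(−a))

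**Example.** Poor risk, median 8 months: λ = 1.040, a = 1.340, r/a = 0.224, bracket = 0.938, so 0.224 × 0.938 = 0.210. Favourable, median 40 months: λ = 0.208, a = 0.508, r/a = 0.591, bracket = 0.836, so 0.494.

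| Measure (poor / intermediate / favourable) | 8/20/40 months | 12/20/30 months |
|---|---|---|
| True rate per year | 0.3 / 0.3 / 0.3 | 0.3 / 0.3 / 0.3 |
| N (%) as planned | 21.0 / 37.0 / 49.4% | 27.7 / 37.0 / 44.5% |
| 12-month cumulative incidence | 16.5 / 21.4 / 23.5% | 19.0 / 21.4 / 22.8% |
| Poor/favourable ratio, N (%) | 0.43 | 0.62 |
| Poor/favourable ratio, 12 months | 0.70 | 0.83 |

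**True poor-risk rate doubled (0.6 v 0.3).** N (%) gives 34.7% v 49.4% (reversed), or 43.4% v 44.5% (hidden). The 12-month cumulative incidence gives 29.5% v 23.5%, or 33.7% v 22.8%, so the excess is visible. N (%) shows poor-risk patients as worse only above a true rate ratio of 3.66 (8 v 40 months) or 2.09 (12 v 30).

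**Sensitivity, by formula or simulation (8/20/40 months unless stated).**
- Rate 0.6 in year 1 then 0.15: N (%) 31/44/53%. Rate 0.15 then 0.6: 18/39/54%. A single crude rate over all follow-up also drifts between strata (0.50/0.40/0.35 and 0.25/0.32/0.36). Rates by year recover the true value in each.
- All patients survive and are observed for 3 months: 27/42/53%; with 12/20/30 months, 33/42/48%.
- Table 1, Option 2, where the middle group needs only that "at least one risk factor criterion is met". With assumed mixtures, poor / at least intermediate / appear favourable: 21/32/39%; closer medians 28/34/38%. The break-even rate ratio falls to 2.38 or 1.61.
- Rate 1.0 per year, 12 v 30 months: 56% v 73%, ratio 0.77 rather than 0.62.
- Infections clustered before death (0.15 per year, rising to 1.5 in the last 6 months of life): N (%) 43/50/53%, but 12-month cumulative incidence 33/26/21%. The gap in N (%) narrows, yet its order is the opposite of the 12-month order.

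**The case against.** The strongest reply is that N (%) is a legitimate description of what was recorded, that 7.7.4 names no contrast, test or model between strata, and that overall survival by IMDC category is also reported, so readers can see that survival differs. This stands as far as it goes, and it limits the harm to interpretation. It does not remove the problem, because the plan requires the percentages to be split by IMDC category and gives nothing beside them to adjust for observation time.

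A reader might infer that N (%) understates poor-risk morbidity in absolute terms. The calculation does not support that: the poor-risk 21.0% is above its own 12-month cumulative incidence of 16.5%. The distortion lies between strata.

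A reader might also infer that medication use certainly has no patient-year figures. Table 2 assigns medications to secondary objective 2 as well, while the list in 7.7.5 does not name them, so coverage of antibiotic and antihypertensive use is unclear. Procedures are covered in 7.7.5; infection and hypertension diagnoses are not.

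Finally, a reader might extend the point to the before/after comparison, since the look-back also uses all available data. Figure 1 illustrates the study time windows and is not visible in the text reviewed. It may fix those windows, so that extension is not claimed.

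**Conclusion.** The point holds as a defect in how strata can be compared. The mechanism follows from the plan's own definitions: an ever-recorded proportion, variable follow-up that ends at death, and strata built from predictors of survival. The size does not come from the documents. Under the assumptions shown, equal rates appear as 21/37/49% or 28/37/45%, and a doubled poor-risk rate appears as 35% v 49% or 43% v 44%. The distortion is smaller with higher event rates, closer survival, Option 2 grouping or clustering near death.

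These figures concern infections and antibiotic use. No size is claimed for hypertension or antihypertensive use, which may often be present at index. Because the output is secondary, descriptive and untested, this should be corrected but does not threaten the study's main results.

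**What to change.** Amend 7.7.4, by IMDC stratum:

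- **Infections and antibiotic use:** add cumulative incidence at a common time from index (for example 12 months) with death as a competing event. Also add first events per patient-year in the first year, with bootstrap confidence intervals as in 7.7.5 and later years merged if sparse. State that the two answer different questions: the first is lower where death comes first, even at equal rates. Avoid one crude rate over all follow-up.
- **Hypertension and antihypertensive use:** report prevalence at index separately from new onset after index.
- **N (%):** keep it, with median follow-up per stratum beside it.
- **Medications:** state whether the patient-year scaling in 7.7.5 covers them, so that it agrees with Table 2.

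The cost is some wording and a little more analysis of dated records the plan already collects. The drawback is imprecision in small strata and later periods. Under 0.3 per year and 8/20/40 months, 24/45/55% are still at risk at the start of year 2 and 6/20/30% at the start of year 3. An illustrative poor-risk stratum of 60 would leave about 14 (60 × 0.24) and 4 (60 × 0.06), which is why the request centres on the first year.

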6.2. Secondary objectives

1. Assess morbidity of metastatic RCC including
 - a. co-diagnoses and procedures
 - b. infections and antibiotic use
 - c. antihypertensive use before and after mRCC diagnosis, as applicable

2. Assess speciality care healthcare resource use (absolute, per patient, per patient year)
 - a. cumulatively over time from diagnosis
 - b. by treatment line

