7.5. Study size

The expected number of patients eligible for this study is approximated based on publicly available data from the Finnish Cancer registry (<https://syoparekisteri.fi/tilastot/tautitilastot/>):

- In HDSF, there have been approximately 1,100 RCC patients during 2010-2021.
- 20-50% of RCC patients develop advanced/metastatic disease [9] and therefore, the size of mRCC-patient cohort is approximately 220-550 patients.

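### If the low-coverage option in Section 7.7.4 is used, antibiotic and antihypertensive use are no longer reported on their own, although Section 6.2 names both as results

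*Combined protocol and SAP*

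**What the plan says.** Section 6.2 lists, under morbidity, "infections and antibiotic use" (1b) and "antihypertensive use before and after mRCC diagnosis, as applicable" (1c). In 1c, drug use is the outcome itself and not a stand-in for a diagnosis.

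By default, Section 7.7.4 follows this. It lists ICD-10 co-diagnoses (with infections and hypertension singled out), kidney procedures, and use of antibiotics and antihypertensives as separate morbidities. They are assessed at baseline and during follow-up, and "The number (N) and proportion (%) of patients with each morbidity will be reported".

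The same section then adds an option: "If data coverage seems low, use of antibiotics and antihypertensives can be used as a proxy for infections and hypertension, respectively", to be used together with the ICD-10 data. The consequence is given in the next sentence: "Therefore, diagnoses and medications will be analyzed as a combination instead of separately". The plan gives no threshold for low coverage and does not write out the rule for combining a code with a drug record.

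**The concern.** The option is meant to repair under-recorded diagnoses, but as written it also removes the drug-use results. One combined proportion replaces two, and one of those two is what 1c asks for and half of what 1b asks for. No other section restores the separate rows, and Annex 1 lists no stand-alone document that could.

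Two things are at stake. First, a named secondary objective can drop out of the report on a judgement made after the data are seen. Second, the combined figure mixes coded disease with drug use of any indication. A reader who sees only that figure cannot judge whether it corrects under-coding or adds people without the condition.

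**Working it through.** **The plan's own figure.** The only size figure is the expected mRCC cohort. Section 7.5 says "In HDSF, there have been approximately 1,100 RCC patients during 2010-2021" and that 20-50% develop advanced or metastatic disease. 1,100 × 0.20 = 220 and 1,100 × 0.50 = 550, which reproduces the stated 220-550. The point does not depend on it. Objective 1 is descriptive, so no power calculation is involved.

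**Step 1: what is lost.** Let D be the proportion with a code in a window, U the proportion with the drug, and C the proportion with either. Either/or is an inference here. It is the natural reading, because requiring both would count fewer patients than codes alone and could not remedy low coverage. If only C is reported, U is known only to lie between 0 and C.

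**Step 2: effect on 1c (all inputs assumed).** Use rises from 30% to 50%, a true change of 20 points, with the same D in both windows. If code and drug are independent, C = 1 − (1 − D)(1 − U). If the smaller group lies wholly inside the larger, C = max(D, U).

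| D | C before → after, independent | Change | C before → after, nested | Change |
|---|---|---|---|---|
| 20% | 44% → 60% | 16 | 30% → 50% | 20 |
| 40% | 58% → 70% | 12 | 40% → 50% | 10 |
| 60% | 72% → 80% | 8 | 60% → 60% | 0 |

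For D = 60%, independent: 1 − 0.4 × 0.7 = 0.72 and 1 − 0.4 × 0.5 = 0.80. In the nested case C is 60% in both windows whether use rises from 30% to 50%, stays at 30%, or falls from 50% to 30%. The masking occurs among patients who have a hypertension code in the same window as the drug.

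**Step 3: direction of error in the combined figure (all inputs assumed).** Let p be the true prevalence, s the share of true cases that are coded, and u₁ and u₀ the drug use in true cases and non-cases. False codes are ignored, and coding and drug use are taken as independent within true cases. Codes alone give p·s. The combined measure gives C = p[1 − (1 − s)(1 − u₁)] + (1 − p)u₀. With s = 0.30 and u₁ = 0.80, the bracket is 1 − 0.7 × 0.2 = 0.86.

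| True p | u₀ | Codes alone | Combined |
|---|---|---|---|
| 40% | 5% | 12% | 0.4 × 0.86 + 0.6 × 0.05 = 37.4% |
| 20% | 40% | 6% | 0.2 × 0.86 + 0.8 × 0.40 = 49.2% |

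In the first row the combined figure is 2.6 points too low and codes alone are 28 points too low. In the second the combined figure is 29.2 points too high and codes alone are 14 points too low. Over p = 20-40%, s = 30-60% and u₀ = 5-40%, with u₁ = 80%, codes alone give 6-24% and the combined measure 21-61%. The share of counted cases that are true cases runs from 35% to 92%. The documents give none of these inputs, so the direction cannot be settled in advance.

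**The case against.** The strongest reply is that the merge is optional and corrective. The default keeps drug use as a separate morbidity, 1c is itself qualified as applying where feasible, and Section 7.8 requires checks of data coverage with clinical-expert review. When diagnoses are under-coded, adding drug records can bring the figure much nearer the truth, as the first row of Step 3 shows. All of this stands, and it is a good reason to show a combined measure. It gives no reason to withhold the components.

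A reader might infer more than the documents support:

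- **That the merge certainly inflates infection frequency, for instance through antibiotics given around kidney operations.** Hospital medications and kidney procedures are both collected, so this is possible. But the plan gives no figure for it, and Step 3 shows that the error can go either way.
- **That any patient given an antibiotic or antihypertensive becomes a case.** This follows only under either/or, which is not written.
- **That a patient with an old hypertension code and no drug looks the same as one who newly starts a drug.** Section 7.7.4 separates baseline from follow-up, so the two look alike only if code and drug fall in the same window.
- **That these are the study's only safety-type outcomes.** Objective 1a covers other co-diagnoses and procedures, and Section 9 says that product and event cannot be linked for any individual. This is descriptive morbidity.
- **That the merge is unconditional.** The sentence opens by drawing a consequence from the low-coverage condition before it, so the conditional reading is the fair one.

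**Conclusion.** The conflict between Section 6.2 and the low-coverage option in Section 7.7.4 is real, and it follows from the text without any assumed figure. It takes effect only if the option is used. In that case the loss is complete for objective 1c and for the antibiotic-use part of 1b, because the separate proportions are not reported and cannot be recovered from the combined one. The amount of masking (8 or 0 points shown for a true 20 in the 60% example) is illustrative and rests on assumed inputs and the either/or reading. No claim is made that the combined infection or hypertension figure is too high. It may be too high or an improvement, and the plan as written would leave the reader unable to tell.

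**What to change.** In Section 7.7.4, strike the last three words of the sentence that calls for the combined analysis, and add that the following are always reported, before and after index, whatever the coverage:

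- diagnosis-coded infection and diagnosis-coded hypertension, each with N and %;
- antibiotic use and antihypertensive use, each with N and %.

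Show the combined measure only as an additional row, labelled as having a diagnosis or a drug record, so that the rule is explicit. With the components always shown, the undefined coverage trigger no longer decides whether an objective is answered.

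The cost is one amended paragraph and a few more table rows. Diagnoses and medications are already in Table 2, so no new data are needed.
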